13.4 Analysis

The primary endpoint of progression free survival (PFS) and the secondary endpoint of overall survival (OS) will be estimated with Kaplan-Meier curves.¹⁵ Cumulative incidence will be used to estimate the probability of relapse/disease progression treating non-relapse death as a competing risk.¹⁶ Safety measures will be measured descriptively with frequencies and proportions.

13.5 Early Study Stopping Rules – Phase II Component

For phase II component, early stopping rules will be used to monitor the excess toxicity for the additional 12 patients. Stopping rules were developed using Pocock stopping boundaries.¹⁷

Grade 4-5 non-hematologic toxicity by 4 months

Stopping rules were developed for excessive Grade 4-5 non-hematologic toxicity. The goal is to construct a boundary based on toxicity such that the probability of early stopping is at most 10% if the toxicity rate is equal to 10% and our sample size is 12 in phase II component. Given these parameters, the upper stopping boundary for toxicity is 2 events out of 4 patients, 3 out of 10, and 4 at any time. If the true toxicity rate is as high as 40% then the chance of early stopping is 87% and the expected sample size is 6.0.

Grade 4-5 hematologic toxicity lasting for ≥ 7 days by 4 months

Stopping rules were developed for excessive Grade 4-5 hematologic toxicity lasting for ≥ 7 days. The goal is to construct a boundary based on toxicity such that the probability of early stopping is at most 10% if the toxicity rate is equal to 30% and our sample size is 12 in phase II component. Given these parameters, the upper stopping boundary for toxicity is 3 events out of 3 patients, 4 out of 5, 5 out of 8, 6 out of 10, and 7 at any time. If the true toxicity rate is as high as 60% then then chance of early stopping is 75% and the expected sample size is 7.7.

14 Conduct of the Study

14.1 Good Clinical Practice

The study will be conducted in accordance with the appropriate regulatory requirement(s). Essential clinical documents will be maintained to demonstrate the validity of the study and the integrity of the data collected. Master files should be established at the beginning of the study, maintained

for the duration of the study and retained according to the appropriate regulations.

14.2 Ethical Considerations

The study will be conducted in accordance with ethical principles founded in the Declaration of Helsinki. The IRB will review all appropriate study documentation in order to safeguard the rights, safety and well-being of the patients. The study will only be conducted at sites where IRB approval has been obtained. The protocol, consent, written information given to the patients, safety updates, annual progress reports, and any revisions to these documents will be provided to the IRB by the investigator.

Appendix I – Eligibility Checklist

Study of the ADAM17 Inhibitor INCB7839 Combined With Rituximab After Autologous Hematopoietic Cell Transplantation (HCT) For Patients With Diffuse Large B Cell Non-Hodgkin Lymphoma (DLBCL) - HM2013-24

Eligibility Checklist – page 1 of 2

Patient initials

1st 2 initials of first name + 1st 2 initials of last name

Patient ID

Seq #

INCLUSION CRITERIA

A "NO" response to any of the following disqualifies the patient from study entry.

		Yes	No		
1.	Patients 18 years or older who have undergone an autologous hematopoietic cell transplant for the treatment of diffuse large B cell lymphoma with disease response (CR, PR) or stable disease at the day 28 post-transplant reassessment				
2.	Karnofsky Score of $\geq 70\%$				
3.	Able to start the protocol therapy (1st dose of rituximab) between day 28-75 post-transplant				
4.	Adequate organ function defined as:		 		
	test	requirement		patient value	date
	platelets	$\geq 50,000 \times 10^9/L$		     	  /   /  
	ANC	$\geq 1000 \times 10^9/L$ unsupported by G-CSF or GM-CSF for 3 days		   	  /   /  
	renal function	creatinine < 1.5 mg/dl or glomerular filtration rate > 50 ml/min		 .    . 	  /   /  
	AST	$< 3 \times$ UNL		   	  /   /  
	ALT	$< 3 \times$ UNL		   	  /   /  
	total bilirubin	< 3.0 mg/dl (if total bilirubin is ≥ 3.0 patient is eligible if direct bilirubin is WNL)  if direct bili is used		 .  	  /   /  
	pulmonary function	clinically no evidence of pulmonary disease		  /   /  	  /   /  
cardiac function	no symptoms of uncontrolled cardiac disease	  /   /  	  /   /  		
5.	If post-transplant consolidation radiation therapy is given, the patient must be at least 14 days between last radiation treatment and 1st dose of rituximab  check if n/a				
6.	Able to take daily aspirin for the duration of INCB7839 treatment and 1 week after the last dose to reduce the risk of thrombosis (unless of warfarin or LMWH at the time of treatment start)				
7.	Females are either postmenopausal for at least 1 year, are surgically sterile for at least 3 months, or must agree to take appropriate precautions to avoid pregnancy (with at least 99% certainty) from screening through 12 months after the last dose of rituximab if of childbearing potential. Males must agree to take appropriate precautions to avoid fathering a child (with at least 99% certainty) from screening through 12 months after the last dose of rituximab.				
8.	Voluntary written consent signed before performance of any study-related procedure not part of normal medical care				

Study of the ADAM17 Inhibitor INCB7839 Combined With Rituximab After Autologous Hematopoietic Cell Transplantation (HCT) For Patients With Diffuse Large B Cell Non-Hodgkin Lymphoma (DLBCL) - HM2013-24

Eligibility Checklist – page 2 of 2

Patient initials

Patient ID

EXCLUSION CRITERIA

A "YES" response to any of the following disqualifies the patient from study entry.

		Yes	No
9.	Pregnant or breast feeding - Females of childbearing potential must have a blood test or urine study within 14 days prior to enrollment to rule out pregnancy  check if n/a		
10.	Recent venous thrombosis within 4 weeks prior to study enrollment. Patients at high risk for thrombotic events due to inherited risk factors (i.e. factor V Leiden) or DVT/PE in the past 12 months should be on secondary prophylaxis with anti-coagulant therapy (i.e. warfarin or low molecular weight heparin) prior to enrollment  check if n/a		
11.	Active uncontrolled infection		
12.	Active CNS disease		
13.	Previous severe or life-threatening allergic reaction with rituximab or known allergy to the compounds found in INCB7839		
14.	Any gastrointestinal condition causing malabsorption or obstruction (eg, celiac sprue, gastric bypass surgery, strictures, adhesions, history of small bowel resection, blind loop syndrome)		
15.	Unwilling or unable to swallow tablets BID		
16.	Serologic or clinical evidence of current active hepatitis B or C infection, defined as elevated levels of Hep B antigen or Hep C antibody (unless active infection is ruled out by nucleic acid tests)		
17.	known HIV infection		

Having obtained consent and reviewed each of the inclusion/exclusion criteria, I verify that this patient is eligible.

Signature of enrolling investigator

Date

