The primary goal of the dose finding phase is to determine the maximum tolerated dose (MTD) of INCB7839. Up to three dose levels of INCB7839 will be tested (100 mg bid, 200 mg bid, and 300 mg bid). As the 300 mg bid has been proven safe in the non-transplant setting, dose escalation will follow a Fast-Track Design with 1 patient enrolled per dose level until a grade 2 or greater treatment emergent adverse event occurs. A treatment emergent adverse event is any event not present prior to the initiation of the treatment (INCB7839) or any event already present that worsens in either intensity or frequency following exposure to the treatment. At that point, dose escalation will convert to a standard 3+3 design with two additional patients enrolled at the same dose level. If dose level 3 is completed without dose limiting toxicity (DLT) in the 1st 3 patients, an additional 3 patients will be enrolled at this level (without the staggering required by the DLT rules) prior to moving to the phase II component. DLT is defined in section 7.2.2 of the protocol.

Once the phase I dose escalation is completed, an additional 12 patients will be enrolled at the MTD (or dose level 300mg bid, if no DLT) to obtain a more detailed toxicity profile as well as a preliminary estimate of progression free survival at 6 months post-transplant. Persons receiving less than 10 weeks of INCB7839 and/or fewer than 2 doses of rituximab will be replaced for the primary endpoint analysis.

Patients will be followed for 1 year from transplant for progression free survival (PFS) and overall survival (OS).

5 Patient Selection

Study entry is open to patients 18 years and older regardless of gender or ethnic background. While there will be every effort to seek out and include women and minority patients, the patient population is expected to be similar to that of autologous HCT studies at the University Of Minnesota since this is a requirement for study entry.

Inclusion Criteria

- 5.1 Patients 18 years or older who have undergone an autologous HCT for the treatment of DLBCL and are in a complete remission (CR), partial remission (PR) or have stable disease (SD) at the day 28 post-transplant reassessment
- 5.2 Karnofsky Score of $\geq 70\%$ (appendix II)
- 5.3 Able to start the protocol therapy (1st dose of rituximab) between day 28-75 post-transplant
- 5.4 Adequate organ function defined as:

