Hematologic: platelets $\geq 50,000 \times 10^9/L$; ANC $\geq 1000 \times 10^9/L$ unsupported by G-CSF or GM-CSF for 3 days

Renal: creatinine < 1.5 mg/dl or glomerular filtration rate > 50 ml/min

Hepatic: Alanine transaminase (ALT, SGPT) and aspartate aminotransferase (SGOT, AST) < 3 x upper limit of institutional normal and total bilirubin < 3.0 mg/dl (if total bilirubin is ≥ 3.0 patient is eligible if direct bilirubin is within normal limits)

Pulmonary: clinically no evidence of pulmonary disease

Cardiac: no symptoms of uncontrolled cardiac disease

- 5.5 If post-transplant consolidation radiation therapy is given, the patient must be at least 14 days between last radiation treatment and 1st dose of rituximab
- 5.6 Able to take daily aspirin (325 mg) for the duration of INCB7839 treatment and 1 week after the last dose to reduce the risk of thrombosis (not applicable if on other anti-coagulant therapy at time of study enrollment – see section 5.11)
- 5.7 Females are either postmenopausal for at least 1 year, are surgically sterile for at least 3 months, or must agree to take appropriate precautions to avoid pregnancy (with at least 99% certainty) from screening through 12 months after the last dose of rituximab if of childbearing potential. (Note: Permitted

methods that are at least 99% effective in preventing pregnancy should be communicated to the participants and their understanding confirmed).

- 5.8** Males must agree to take appropriate precautions to avoid fathering a child (with at least 99% certainty) from screening through 12 months after the last dose of rituximab. (Note: Permitted methods that are at least 99% effective in preventing pregnancy should be communicated to the participants and their understanding confirmed).
- 5.9** Voluntary written consent signed before performance of any study-related procedure not part of normal medical care

Exclusions

- 5.10** Pregnant or lactating – Studies to evaluate the potential for embryo toxicity and teratogenicity have not been performed for INCB7839. Until additional information is available, women of childbearing potential should use appropriate precautions to avoid becoming pregnant. Rituximab is Pregnancy Category C: There are no adequate and well-controlled studies of rituximab in pregnant women. Females of childbearing potential must have a negative urine or serum pregnancy test within 14 days of study treatment start

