- 5.11** Recent venous thrombosis within 4 weeks prior to study enrollment. Patients at high risk for thrombotic events due to inherited risk factors (i.e. factor V Leiden) or DVT/PE in the past 12 months should be on secondary prophylaxis with anti-coagulant therapy (i.e. warfarin or low molecular weight heparin) prior to enrollment
- 5.12** Active uncontrolled infection
- 5.13** Active CNS disease
- 5.14** Previous severe or life-threatening allergic reaction with rituximab or known allergy to the compounds found in INCB7839
- 5.15** Any gastrointestinal condition causing malabsorption or obstruction (eg, celiac sprue, gastric bypass surgery, strictures, adhesions, history of small bowel resection, blind loop syndrome)
- 5.16** Unwilling or unable to swallow tablets BID
- 5.17** Serologic or clinical evidence of current active hepatitis B or C infection, defined as elevated levels of Hep B antigen or Hep C antibody (unless active infection is ruled out by nucleic acid tests)
- 5.18** Known HIV infection

6 Patient Screening and Enrollment/INCB7839 Dose Level Assignment

Written consent must be obtained prior to the performance of any research related tests or procedures. Consent is usually obtained before final eligibility is determined.

Enrollment in the study and the 1st dose of rituximab may occur up to day 75 post-transplant.

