6.2 Study Enrollment

To be eligible for study enrollment, the patient must sign the treatment consent and meet each of the inclusion criteria and none of the exclusion on the eligibility checklist (Appendix I) based on the eligibility assessment documented in the patient's medical record.

The Primary Clinical Research Coordinator (PCRC) or designee will assign the study treatment arm and add the on-treatment date to complete enrollment.

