6.4 Patients Who Are Registered and Do Not Receive Study Treatment

If a patient is registered to the study, and is later found not able to receive the 1st dose of rituximab by day 75 post-transplant, for whatever reason, the patient will be removed from study and treated at the physician's discretion. The PCRC or designee will update OnCore of the patient's non-treatment status and notify the Principal Investigator. Study data will be collected until the time the patient is off study. The reason for removal from study will be clearly in OnCore. The patient will be replaced to complete enrollment.

7 Treatment Plan

The first dose of rituximab will be considered study week 1 regardless of whether it is given at post-transplant day 28 or as late as post-transplant day 75. Routine post-transplant follow-up will continue as planned, independent of this study, although during active treatment study visits will be scheduled to coincide with transplant related visits (i.e. day 60, 100). Follow-up time points for disease and survival status will remain linked with a post-transplant visit at 6 and 12 months regardless of when the 1st dose of rituximab is given.

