11.2 Case Report Forms

Participant data will be collected using protocol specific electronic case report forms (e-CRF) developed within OnCore based on its library of standardized forms. The e-CRF will be approved by the study's Principal Investigator and the Biostatistician prior to release for use. The Primary Clinical Research Coordinator or designee will be responsible for registering the patient into OnCore at time of study entry, completing e-CRF based on the patient specific calendar, and updating the patient record until patient death or end of required study participation.

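### Checklist item 9 counts the 14-day pregnancy-test window from enrollment, while exclusion 5.10 counts it from treatment start, so the form can accept a test older than 5.10 allows if enrollment comes first

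*Combined protocol and SAP*

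**What the plan says.** Two current texts set the timing of the pregnancy test.

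- Exclusion 5.10: a woman of childbearing potential "must have a negative urine or serum pregnancy test within 14 days of study treatment start".
- Appendix I, item 9: "Females of childbearing potential must have a blood test or urine study within 14 days prior to enrollment to rule out pregnancy".

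The start of treatment is identified in 5.3: "Able to start the protocol therapy (1st dose of rituximab) between day 28-75 post-transplant". Section 7 agrees, since it calls the first rituximab dose study week 1.

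On enrollment, section 6.2 admits only patients who pass the Appendix I checklist, and an investigator signs that form to confirm eligibility. Section 6.2 also has the coordinator "add the on-treatment date to complete enrollment". Section 6 states one outer limit for both events: "Enrollment in the study and the 1st dose of rituximab may occur up to day 75 post-transplant". It sets no maximum interval between them. Section 6.4 deals with a registered patient who "is later found not able to receive the 1st dose of rituximab by day 75 post-transplant", and section 11.2 makes the coordinator responsible for "registering the patient into OnCore at time of study entry".

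The section 8.1 table has one pregnancy test, in the screening column. That column runs from day 28 to day 60 post-transplant. Footnote 1 of the table lets Day 1 fall anywhere from day 28 to day 75. No repeat test is marked at Day 1.

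**The concern.** The two rules use the same number of days but count from different events. If enrollment falls before the first rituximab dose, a woman can pass item 9 with a test that is too old under 5.10. Nothing on the form or in the schedule would prompt anyone to notice, because the form looks back from enrollment and the schedule has no test after screening.

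What is at stake is a safety screen. Section 5.10 notes that embryo toxicity and teratogenicity have not been studied for INCB7839, and it cautions on rituximab in pregnancy as well. On this one item, the form that decides entry can be looser than the criterion it is meant to apply.

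**Working it through.** The plan states no figure to reproduce. The check is date arithmetic on the two rules.

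**Notation, in days post-transplant.** t is the day of the test, e the day of enrollment, d the day of first rituximab, and g = d − e the gap between enrollment and first dose.

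**The rules**
- Item 9: e − t ≤ 14.
- 5.10, with treatment start taken as first rituximab (5.3): d − t ≤ 14.

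**Oldest test that item 9 accepts, measured at first dose**

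d − t = (e − t) + (d − e) ≤ 14 + g

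| g (assumed) | Oldest test under item 9 | Limit in 5.10 | Excess |
|---|---|---|---|
| 0 | 14 | 14 | 0 |
| 1 | 15 | 14 | 1 |
| 7 | 21 | 14 | 7 |
| 14 | 28 | 14 | 14 |

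The excess equals g. These are upper limits for each gap. With g = 7, for example, only a test taken more than 14 − 7 = 7 days before enrollment would breach 5.10. The documents do not give g, so the values in the first column are illustrations.

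**Can g be above zero?** Section 6.4 foresees a patient registered but not yet dosed, and 11.2 places registration at study entry, which is the step the checklist controls. This shows indirectly that the two events can be separate. It does not show that they usually are. If the on-treatment date in 6.2 is Day 1 and enrollment is complete only when it is entered, then g = 0.

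**The schedule, taken separately.** This part does not depend on g.
- Latest screening day in the 8.1 column: 60. Latest Day 1 in footnote 1: 75. Since 75 − 60 = 15 > 14, a Day 1 on day 75 read literally uses a screening test at least 15 days old.
- More generally, 8.1 sets no limit on the time from screening to Day 1. A test on day 28 followed by Day 1 on day 43 is already 43 − 28 = 15 days old.

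Two readings remove the day-75 case. If the ±3-day window in section 8 also covers screening, the last screening day becomes 63 and 75 − 63 = 12. If the day-60 limit for first rituximab that still stands in section 7.1 governs, Day 1 cannot fall after day 60. Neither reading removes the second case.

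**INCB7839.** By sections 7.1 and 7.2 this drug starts with the second rituximab dose, 1 week ± 3 days after the first. A test that fully complies with 5.10 can therefore be 14 + 7 = 21 days old at first INCB7839, and up to 14 + 10 = 24. A positive g adds to that interval but does not create it.

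**After the fix.** With item 9 counted from first rituximab, the limit at first dose is 14 days whatever g is.

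**The case against.** The strongest reply is that there may be no gap. The only statement on how enrollment is completed is in 6.2, and it ties completion to an on-treatment date. On that reading a patient under 6.4 has been registered but has not finished enrolling, and the two rules coincide. The drafters may also have used the two terms loosely: 5.6 refers to anticoagulant use at enrollment where checklist item 6 refers to treatment start. This stands as a limit on the effect. It does not remove the mismatch, because no section defines the two events as one.

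Second, 5.10 is a criterion in its own right and pregnancy excludes a woman under either text. Contraception with at least 99% certainty applies from screening (5.7), and 7.1 intends dosing on or soon after the day-28 re-assessment. All of this stands, and it keeps the point minor.

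Third, it can be said that a footnote in 8.1 only restates 5.10. That is partly right, but the schedule as printed permits a sequence that 5.10 forbids, so the reminder has a purpose.

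A reader might go further and infer that women were routinely dosed on tests many weeks old, or that most permitted start days are exposed. The documents do not support this. They give no enrollment-to-dose interval, and a count of calendar days says nothing about how many patients start on them. A reader might also infer that the mismatch is what exposes patients to untested INCB7839 risk. It is not, because 5.10 itself accepts a test about three weeks old when that drug begins.

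**Conclusion.** The mismatch is real and is in operative text. Item 9 can be satisfied by a test 14 + g days old at first rituximab, against 14 days in 5.10. The effect is conditional on g being at least one day, which the documents allow but do not quantify; if g = 0 there is none. The schedule in 8.1 is a second, independent weakness, since it does not by itself ensure that the test is recent enough at Day 1.

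This rests on reading study treatment start as first rituximab, following 5.3. If it meant first INCB7839, the interval after enrollment would be longer by about a week.

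The size is minor. It is an inconsistency between a form and its criterion, and correcting it gives a small safety benefit to women of childbearing potential. No endpoint, analysis or sample size is affected.

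**What to change.** Reword checklist item 9 along these lines: *Negative pregnancy test (urine or serum) taken no more than 14 days before first rituximab.* Checklist item 5 already counts from that dose.

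Add a footnote to the pregnancy-test row in 8.1: if the screening test would be more than 14 days old at Day 1, repeat it before dosing.

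The cost is one line on the form, one footnote and an occasional repeat urine test. With screening from day 28, a repeat can be needed only for first doses from day 43 on (28 + 14 = 42). The change leaves the further week or so before INCB7839 starts as it is.

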INCB007839, a potent and selective inhibitor of ADAM10 and ADAM17, in combination with trastuzumab, improves progression-free survival (PFS) and overall survival (OS) in metastatic HER2-positive breast cancer patients compared to trastuzumab monotherapy. This benefit is observed in patients with more advanced disease, including those with brain metastases. The combination also shows a favorable safety profile.

Results

Despite More Advanced Disease, Trastuzumab + INCB007839 Improves TTP vs. the Historic Control Study of Q.M. Trastuzumab Monotherapy

Median TTP: 10.3 months (95% CI 8.8-11.8) vs. 7.8 months (95% CI 7.1-8.5), p < 0.001

Identification of p95HER2+ Patients in INCB7839-202 Using Digitized IHC

Tumor biopsy specimens were stained for HER2 using antibodies against intracellular (Cy5) and extracellular (Cy3) HER2 epitopes. Digital analysis was performed using the QuPath software. Patients with a score of 15 or greater were considered p95HER2 positive.

Clinical Benefit in the p95 Subpopulation of HER2+ Patients

Significant Decreases in HER2 ECD Induced by INCB007839 Associates with Clinical Benefit

INCB007839 May Show Benefit by Inhibiting EGF Ligand Cleavage and Generation of Soluble Active EGF Ligand

Adverse Events

- Generally well tolerated
- No EGFR kinase related toxicities (rash)
- No MMPI related toxicities (musculoskeletal)
- No drug related liver enzyme elevations
- No drug related bone marrow toxicities
- No increase in cardiomyopathy
- 546 patients experienced cardiomyopathy (11%)
- No increase in thrombotic events
- 546 patients experienced a thrombotic event (11%)

Study Design/Enrollment

INCB 7839-202, A Phase 1b, Modified Dose Escalation, Open Label, Randomized, Therapeutic Study and Trastuzumab + INCB007839 Combined with Trastuzumab in Patients with Previously Untreated Metastatic HER2 Positive Breast Cancer

Enrollment in 7839-202 by Dose Level	n	Confirmed HER2+	Evaluable HER2+
300 mg	0	4	4
200 mg	0	6	6
100 mg	27	27	21
Total	27	37	31

INCB7839 Significantly Inhibits HER2 Shedding

INCB007839 Produces a Rapid and Dose-dependent Inhibition of Plasma ECD

Trastuzumab + INCB007839 Improves PFS in p95HER2+ Patients

INCB007839 Produces a Rapid and Persistent Inhibition of Plasma ErbB Ligand Levels

Continued INCB007839 Administration Produces a Persistent Suppression of Circulating ECD Levels

Trastuzumab + INCB007839 Improves Response Rate and Overcomes Trastuzumab Resistance in p95HER2+ Patients

